#### 1.2.5.3. Safety Parameters

The safety endpoints include AEs, SAEs, and injection site reactions (ISRs), and laboratory parameters (including pregnancy testing), vital signs, ECG recordings, physical examination findings, skin examination, and the Columbia-Suicide Severity Rating Scale (C-SSRS) questionnaire results.

## **2. PATIENT POPULATION**

### **2.1. Population Definitions**

The following patient populations will be evaluated and used for presentation and analysis of the data:

- **Pharmacokinetic Analysis Set (PKAS):** All patients who receive at least 1 dose of setmelanotide and who have a sufficient number of measurable plasma concentrations to permit assessment of noncompartmental parameters.
- **Full Analysis Set (FAS):** All patients who receive at least 1 dose of setmelanotide after the randomization. Patients will be analyzed according to their randomly assigned treatment.
- **Per Protocol Set (PPS):** All patients in the FAS without any major protocol violations that would result in exclusion of the patients from the analysis. Patients will be analyzed according to their randomly assigned treatment.
- **Safety Analysis (SA) Set:** All patients who receive at least 1 dose of protocol-specified study drug. Patients will be analyzed according to the treatment they actually received.

The FAS is the primary population for the analysis of [REDACTED] parameters. A subset of [REDACTED] parameters will be evaluated for the PPS (see [Section 4.3](#)). The SA set is the primary population for the analysis of safety endpoints.

### **2.2. Protocol Violations**

At the discretion of the Sponsor, major protocol violations, as determined by a review of the data prior to unblinding of the study results and the conduct of statistical analyses, may result in the removal of a patient's data from the PPS. Any type of dose adjustment will be captured as a protocol violation. The Sponsor or designee will be responsible for producing the final protocol violation file (formatted as a Microsoft Excel file), in collaboration with [REDACTED] and the data monitoring group, as applicable. This file will include a description of the protocol violation and clearly identify whether or not this violation warrants exclusion from the PPS. This file will be finalized prior to hard database lock.

All protocol violations will be presented in a data listing.

### **3. GENERAL STATISTICAL METHODS**

#### **3.1. Sample Size Justification**

The sample size is based on availability of the patients enrolled in the LTE study and is not driven by formal statistical hypothesis testing on non-inferiority/similarity.

#### **3.2. General Methods**

All data listings that contain an evaluation date will contain a relative study day (Rel Day). Pre-treatment and on-treatment study days are numbered relative to the day of the first dose of study vaccine which is designated as Day 1. The preceding day is Day -1, the day before that is Day -2, etc. The last day of study medication is designated with an “L” (e.g., Day 14L). Post-treatment study days are numbered relative to the last dose and are designated as Day 1P, Day 2P, etc.

All output will be incorporated into Microsoft Word or Excel files, or Adobe Acrobat PDF files, sorted and labeled according to the International Conference on Harmonisation (ICH) recommendations, and formatted to the appropriate page size(s).

Tabulations will be produced for appropriate demographic, baseline, [REDACTED] PK, and safety parameters. For categorical variables, summary tabulations of the number and percentage of patients within each category (with a category for missing data) of the parameter will be presented. For continuous variables, the number of patients, mean, median, standard deviation (SD), minimum, and maximum values will be presented. Summarizations will be created for the groups of setmelanotide, genetic subgroups, and age groups.

This study is primarily descriptive in nature; therefore, there are no formal statistical hypothesis tests planned. Data will be presented by patient and summarized by QD/QW as well as genetic subgroup or by age group depending on the analysis. Summary statistics will be presented, as well as confidence intervals (CIs) on selected parameters, as described in the sections below.

#### **3.3. Computing Environment**

All descriptive statistical analyses will be performed using SAS statistical software Version 9.4, unless otherwise noted. Medical history and AEs will be coded using the Medical Dictionary for Regulatory Activities (MedDRA) Version 24.0 or later. Prior and concomitant medications will be coded using the World Health Organization (WHO) Drug Dictionary Version March 1, 2021 or later.

#### **3.4. Baseline Definitions**

For all [REDACTED] analyses, baseline will be defined as the following: the last value prior to randomization in the 13-week double-blind period.

For safety parameters including key laboratory (e.g., hematology and chemistry) data, the last value obtained prior to the first dose of setmelanotide or placebo in RM-493-037 will be used as the baseline. For the C-SSRS analysis, the baseline assessment that was collected at the beginning of the index study [REDACTED] should continue to be used as the baseline for this study.

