8.8.9.1. Columbia-Suicide Severity Rating Scale

As required in the US by the Food and Drug Administration (FDA), for clinical trials of CNSacting medications, changes in depression/suicidality as assessed by the C-SSRS will be monitored over the course of the trial to ensure patient safety.

The C-SSRS is a tool used not only to predict suicide attempts but to assess the full range of evidence-based ideation and behavior items, with criteria for next steps (e.g., referral to a MHP). There are 2 versions of the C-SSRS that will be administered:

• The **Screening** version of the scale documents recent (within the past month) scores from the screening C-SSRS scale. This version can assess a patient's eligibility based on inclusion/exclusion criteria.

[Note that patients will have completed the Baseline/Screening version of the C-SSRS scale during the index trial and are therefore not expected to complete this version in the current trial. **Thus, the baseline assessment that was collected at the beginning of the index trial should continue to be used as the baseline for this trial.** (The Baseline/Screening version of the scale combines the Baseline and Screening forms to assess suicidality in a patient's lifetime and during a predefined time period. This version can assess a patient's lifetime suicidality for data collection

purposes as well as eligibility, based on inclusion/exclusion criteria, for the index trial.)]

• The Since Last Visit version of the scale assesses suicidality since the patient's last visit. This version is meant to assess patients who have completed at least 1 initial C-SSRS assessment and should be used in every subsequent visit. The 'Since Last Visit' version of the C-SSRS is asking about any suicidal thoughts or behaviors the patient/participant may have had since the last time you have administered the C-SSRS.

To be eligible for the trial, a patient cannot have suicidal ideation of type 4 or 5, any lifetime history of suicide attempt, or any suicidal behavior in the last month in patients with no significant neurocognitive deficits.

Pediatric patients may not be able to complete the C-SSRS as intended. If in the clinical opinion of the Investigator a specific patient cannot complete the instrument, the following strategies may be employed:

- Site staff may administer the questions directly to the patient or may ask for the information from a third party, such as a caregiver or family members, as appropriate.

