 The Baseline/Screening version of the C-SSRS should only be administered to patients who have never completed an initial C-SSRS assessment prior to entering this trial; however, this version is expected to have been completed in the index study for all patients prior to entry into this study. The Screening version of the C-SSRS is to be completed at the Screening visit. At all subsequent visits, the Since Last Version is to be completed. If at any time during the study a patient has suicidal ideation of type 4 or 5, or any suicidal behavior, the patient should be referred to a mental health professional.

 The dosing diary will be completed for all QD and QW dose administration.

[REDACTED]

 Prior to the QW dose of study drug, a blood sample for trough plasma levels of setmelanotide will be drawn within 10 minutes prior to dosing. On the days when 24-hour PK profiles (including optional timepoint at 12 hours after dosing) are done, the predose (trough) PK sample will be drawn within 5 minutes prior to study drug administration. The trough sample to be drawn at Week 14 (V16) will be used as the 168-hour postdose sample for the purpose of the PK profile, therefore no visit window is allowed for Week 14, which must occur exactly 7 days after the last dose of double-blind QW study drug. Patients/caretakers will be reminded that there should be NO study drug administration at home on the day of clinic visits; the drug will be administered in the clinic AFTER the PK sample is obtained. For the PK sample, the actual collection (clock) time will be recorded, as well as the time of the previous day's study drug injection as reported by the patient/caretaker.

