#### 4.5.9. Columbia Suicide Severity Rating Scale

The C-SSRS will be measured as shown in the SoA ([Table 1](#)) according to the age of the patient (child <12 or adult  $\geq$ 12). Results of the C-SSRS will be provided in a shift table assessing shifts from the baseline most severe ideation to most severe ideation during follow-up. A by-patient listing including the ideation, intensity of ideation, behavior, and number of attempts will be provided.

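### The C-SSRS shift table measures change from the start of the index trial, so it can misplace ideation relative to this trial's switch to QW

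*SAP*

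**What the plan says.** SAP 3.4 sets two safety baselines. Laboratory and other safety parameters use the last value before the first dose of setmelanotide or placebo in RM-493-037. The C-SSRS is the exception: its baseline is "the baseline assessment that was collected at the beginning of the index study". Protocol 8.8.9.1 agrees: "the baseline assessment that was collected at the beginning of the index trial should continue to be used as the baseline for this trial". According to that section, the form used at that time "combines the Baseline and Screening forms to assess suicidality in a patient's lifetime and during a predefined time period".

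The summary analysis in SAP 4.5.9 is a "shift table assessing shifts from the baseline most severe ideation to most severe ideation during follow-up", with a by-patient listing. The section does not define follow-up, states no split by period, and does not say which recall part of the index form supplies the baseline.

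This trial collects its own C-SSRS data before randomization. A footnote to SAP Table 1 states: "The Screening version of the C-SSRS is to be completed at the Screening visit". Protocol 8.8.9.1 says that this version "documents recent (within the past month) scores from the screening C-SSRS scale". The same footnote continues: "At all subsequent visits, the Since Last Version is to be completed". The Schedule of Activities places predose forms at Visit 2 (Run-in) and Visit 3 (Day 1).

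**The concern.** The secondary objective is the safety of the QW formulation, studied by switching patients who are stable on QD. The natural reference for a change in suicidality is the patient's state just before randomization. The planned reference comes from before the index trial, and inclusion criterion 3 requires at least 6 months of QD in the LTE after that. Anything that changed in between, in either direction, is counted as if it had happened in this trial or cancels against what did happen.

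At stake is how the C-SSRS table in the study report is read. A reader will take it as evidence on the QW formulation. As defined, it describes change since a patient first entered the setmelanotide programme.

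**Working it through.** The plan states no figure for this point, so there is nothing to reproduce. The check is logical.

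**Inputs.** Code most severe ideation as 0 (none) or types 1 to 5. The documents name types 4 and 5; the full coding is an assumption.
- I = index-trial baseline (SAP 3.4, Protocol 8.8.9.1).
- S = most severe ideation before randomization in this trial. Types 4 and 5 are excluded at entry (Protocol 6.2, criterion 7), so S is taken as 0 to 3.
- F = most severe ideation on study (SAP 4.5.9).

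**Rules.** Ideation has risen in this trial if F > S. The planned table shows worsening only if F > I. Hence:
- missed rise: S < F ≤ I
- false worsening: I < F ≤ S

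**Examples.**

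| I | S | F | Planned table | From this trial's baseline |
|---|---|---|---|---|
| 3 | 0 | 3 | 3 to 3, no change | 0 to 3, worsening |
| 0 | 2 | 2 | 0 to 2, worsening | 2 to 2, no change |
| 0 | 0 | 3 | 0 to 3, worsening | 0 to 3, worsening |

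The third row shows the limit: a patient with no ideation at the index baseline cannot have a rise missed.

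**Pattern counts.** These are counts of logical combinations, not probabilities.
- Rises: for each I, the pairs with F > S number 5 + 4 + 3 + 2 = 14. Over I = 0 to 5 this gives 6 × 14 = 84.
- Missed rises for I = 0, 1, 2, 3, 4, 5: 0 + 1 + 3 + 6 + 10 + 14 = 34 of 84.
- If the exclusion of types 4 and 5 also caps the index value at 3: 0 + 1 + 3 + 6 = 10 of 4 × 14 = 56, all at types 1 to 3.
- With S = 0 and I = 0 to 5: 0 + 1 + 2 + 3 + 4 + 5 = 15 of 6 × 5 = 30.
- No rise: for each I, the pairs with F ≤ S number 1 + 2 + 3 + 4 = 10, so 60 over six values of I. False worsening for S = 0, 1, 2, 3: 0 + 1 + 3 + 6 = 10 of 60.

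With S as the baseline, both kinds of error are zero by construction.

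**Period.** The protocol's Schedule of Activities gives C-SSRS forms at Weeks 5, 9 and 14 (predose), which cover the double-blind period. Weeks 18, 22 and 27 (predose) cover open-label QW, and Week 30 covers the return to QD. If follow-up means all of these, F in the QD arm is a maximum over QD, then QW, then QD again. A shift in that arm cannot be assigned to a formulation. By contrast, SAP 4.5.2 tabulates adverse events separately for Day 1 to Week 14.

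**The case against.** The baseline is a deliberate rule, stated identically in both documents, and the trial is descriptive with no hypothesis tests. With about 30 patients, the by-patient listing shows each ideation result, and SAP 3.2 adds a relative study day to listings that carry an evaluation date. A suicidality event recorded as an adverse event would also appear in the SAP 4.5.2 tables without reference to any C-SSRS baseline. PHQ-9 is summarized by visit. All of this stands, and it limits the point to a single table.

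Five stronger readings are tempting, and the documents do not support them.
- **The baseline is a lifetime worst.** Protocol 8.8.9.1 says the form covers lifetime and a predefined period, and neither document says which part is used. The point does not need the lifetime reading, because both parts predate the LTE treatment.
- **This is the only summary of suicidality.** Adverse event tables may also capture it, as noted above.
- **The table is not split by treatment.** SAP 4.5.9 is silent, but SAP 3.2 and 3.5 plausibly supply a QD/QW split. Only the period split is missing.
- **A definite number of patients is masked.** An assumed prevalence of 10% to 30% among 30 patients would give 3 to 9. That range has no source in the documents, and those patients would only be open to masking. A recurrence at or below the index level is also needed.
- **Patients are less protected.** Referral to a mental health professional for ideation of type 4 or 5, suicidal behavior or a PHQ-9 score of 10 or more does not depend on the baseline.

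The cap of the index value at 3 is also uncertain. The exclusion of types 4 and 5 states no time limit, and Protocol 8.8.9.1 words it for patients without significant neurocognitive deficits. If it covers only recent ideation, or does not apply to a given patient, the index value can be higher.

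**Conclusion.** The concern holds as a weakness in one analysis, not as a contradiction between protocol and SAP. Followed as written, the SAP 4.5.9 table can hide ideation that is new since this trial's Screening and can report ideation from before this trial as worsening. Without a period split, it also cannot tie a shift in the QD arm to a formulation after Week 14.

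The logic requires only that the index assessment predates the LTE treatment, which both documents make clear. Its size in patients is unknown, because the documents give no distribution of index or Screening ideation. It deserves correction because the remedy is nearly free and fits the QW safety objective better.

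**What to change.** Add to SAP 4.5.9:
1. A shift table by randomized group. The baseline is the worst ideation on the Visit 1 Screening form (past month) and the predose Since Last Visit forms at Visits 2 and 3. The outcome is the worst ideation from after the Day 1 dose to the predose Week 14 assessment.
2. A second table by randomized group, from the same baseline, for the open-label QW period, ending with the predose Week 27 assessment.
3. The existing index-baseline table kept as supportive, with a statement of which recall part of the index form it uses and what follow-up covers.

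No new data are needed. Protocol 9 lets the SAP modify planned analyses and asks for an amendment only for major changes to the primary endpoint or its analysis, so a SAP revision should suffice.

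The cost is one or two tables. The drawback is unequal look-back: a past-month form set against repeated assessments over 13 weeks favours apparent worsening. In the double-blind period this applies equally to both arms, so table 1 should be read as a comparison between arms. Table 2 has no concurrent QD control and is descriptive only.

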### **3.5. Methods of Pooling Data**

There will be two groups pooled to categorize the setmelanotide treatments so that differences between QD/QW can be easily seen: QW and QD. The QD group includes those patients who were randomized to QD setmelanotide in the randomized double-blind treatment period (Period 1) and QW setmelanotide in the open-label period (Period 2). The QW group includes those patients randomized to QW setmelanotide in the randomized double-blind treatment period (Period 1) and in the open-label period (Period 2).

Summary tabulations may be pooled across genetic obesity disorder populations as available.

In certain cases, tabulations will be stratified by age group ( $\geq 6$  to  $< 12$  years old,  $\geq 12$  to  $< 18$  years old,  $\geq 18$  years old). All of these patients must have participated in the extension study, RM-493-022.

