9.1. Sample Size Determination

The primary objective is to assess steady-state PK parameters (maximum plasma concentration $[C_{max}]$, time to maximum plasma concentration $[T_{max}]$, trough plasma concentration $[C_{trough}]$, area under the plasma concentration-time curve over the dosing interval $[AUC_{0-tau}]$) for QW compared with QD setmelanotide. The sample size is based on availability of the patients enrolled in the LTE trial and is not driven by formal statistical hypothesis testing on non-inferiority/similarity.

9.2. **Populations for Analyses**

The analysis populations are defined as follows:

- Pharmacokinetic Analysis Set (PKAS): All patients who receive at least 1 dose of setmelanotide and who have a sufficient number of measurable plasma concentrations to permit assessment of noncompartmental parameters.
- Full Analysis Set (FAS): All patients who receive at least 1 dose of setmelanotide. Patients will be analyzed according to their randomly assigned treatment.

- Per Protocol Set: All patients in FAS without any major protocol violations that would result in exclusion of the patients from the analysis. Patients will be analyzed according to their randomly assigned treatment.
- Safety Analysis Set: All patients who are randomized and receive at least 1 dose of protocol-specified study drug. Patients will be analyzed according to the treatment they actually received.

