## **4.5. Safety Analyses**

Safety analyses will be conducted using the SA Set.

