### **4.5.1. Drug Exposure**

Drug exposure will be summarized by QD/QW treatment group across the entire length of the study. The number of doses administered, total dose received in mg, treatment duration in weeks, and percentage of dosing compliance will be summarized using descriptive statistics (N, mean, SD, median, minimum, maximum, and 95% confidence intervals). Treatment duration will be defined in weeks as  $(\text{date of last dose} - \text{date of first dose} + 1) / 7$ . Dosing compliance percentage will be defined as  $([\text{number of doses administered}] / [\text{duration of treatment in days}]) * 100$  for QD treatment and  $([\text{number of doses administered} * 7] / [\text{duration of treatment in days}]) * 100$  for QW treatment. A by-patient listing for dosing will be created.

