### **4.5.2. Adverse Events**

All AEs will be coded using the MedDRA coding system (Version 24.0 or later) and displayed in tables and data listings by SOC and PT. Adverse events will also be graded using the National Cancer Institute Common Terminology Criteria for AEs (NCI-CTCAE) on a scale of Grades 1 to 5 in which Grade 1 is a mild AE, Grade 2 a moderate AE, Grade 3 a severe AE, Grade 4 a life-threatening or disabling AE, and Grade 5 a fatal AE). Those not listed by CTCAE will be graded as either mild, moderate, or severe.

Analyses of AEs will be performed for those events that are considered treatment-emergent, where treatment-emergent is defined as any AE with onset after the administration of randomized study medication at the start of the Run-in period through the end of the study (at the end of the 3-week follow-up period), any event that was present at baseline (beginning of Run-in period) but worsened in intensity or was subsequently considered drug-related by the Investigator through the end of the study, or any event deemed to be related to study drug exposure.

The number and percentage of patients with any treatment-emergent adverse event (TEAE), with any TEAE assessed by the Investigator as related to treatment (definite, probable, or possible relationship), with any serious TEAE, any serious related TEAE, with any TEAE resulting in study drug withdrawal, with any TEAE leading to death will be summarized by QD/QW treatment group and overall. All TEAE analyses will have separate tabulations for two time frames: the beginning of the randomized, double-blind period (Day 1) to Week 14 and the beginning of the Run-in period through the end of the 3-week follow-up period (end of study). Since visits are not collected for AEs, the dates that each patient started and ended treatment at

each of these periods will be used to compare to the AE start and end dates for each patient in order to subset on the AEs specific to the randomized, double-blind period.

In these tabulations, each patient will contribute only once (i.e., the most related occurrence or the most intense occurrence) to each of the incidence rates in the descriptive analysis, regardless of the number of episodes.

No formal hypothesis-testing analysis of AE incidence rates will be performed.

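### The full-study TEAE and exposure tables put the QD arm's 13 open-label weeks on QW under a QD heading, and no TEAE summary separately shows the open-label period or all QW exposure

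*SAP*

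**What the plan says.** SAP 3.5 forms two groups, QD and QW, "so that differences between QD/QW can be easily seen". The QD group is those patients "randomized to QD setmelanotide in the randomized double-blind treatment period (Period 1) and QW setmelanotide in the open-label period (Period 2". The QW group takes QW in both periods. Both groups also take QD during the run-in and the 3-week follow-up.

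The exposure and TEAE sections use this group vocabulary. SAP 4.5.1: "Drug exposure will be summarized by QD/QW treatment group across the entire length of the study". SAP 4.5.2 summarises TEAEs by QD/QW treatment group and overall, and adds: "All TEAE analyses will have separate tabulations for two time frames". These are Day 1 to Week 14, and the start of Run-in to the end of follow-up. Within each table, "each patient will contribute only once (i.e., the most related occurrence or the most intense occurrence) to each of the incidence rates".

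SAP 4.5 states: "Safety analyses will be conducted using the SA Set". SAP 2.1 defines that set as: "All patients who receive at least 1 dose of protocol-specified study drug. Patients will be analyzed according to the treatment they actually received". Protocol 9.2 has the same analysis rule: "Patients will be analyzed according to the treatment they actually received". By contrast, the injection site, laboratory and vital-sign sections (SAP 4.5.3 to 4.5.5) refer to treatment received rather than to treatment group.

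The secondary objective (Protocol Section 4, Table 2) is the safety of the QW formulation over up to 26 weeks.

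**The concern.** Every patient is planned to receive QW at some point, and half of them reach it only by switching from blinded QD at Week 14. A reader of the full-study TEAE table would take the QD column as experience on the daily formulation, when a large part of it is experience on the weekly one. That works against the aim stated in SAP 3.5.

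The gap bears on the secondary objective. The full-study QW column covers the patients randomised to QW reasonably well. The QD arm's 13 weeks on QW, including its change of formulation, have no TEAE summary of their own. In a descriptive trial of about 30 patients, with about 10 under 18, column labels and time windows carry most of the interpretation.

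The SAP also does not say how its sequence grouping and its treatment-received rule apply together to a patient who switches regimen, nor to which regimen an event or dose belongs.

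**Working it through.** **Inputs.** Run-in of 1 to 7 days on QD, 13 weeks randomised, 13 weeks open-label QW, 3 weeks on QD (Protocol synopsis, duration of treatment). Visit days 1, 92, 183 and 204 (Schedule of Activities). About 30 patients, randomised 1:1. Assumed here: 15 per arm, no dropout, full adherence.

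**Plan's own figure.** 1 + 13 + 13 + 3 = 30 weeks, matching the stated total of about 30. The visit days agree: 92 − 1 = 91 days, 183 − 92 = 91 days, 204 − 183 = 21 days. Total 7 + 91 + 91 + 21 = 210 days, or 204 days with a 1-day run-in.

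**What the full-study columns contain, if SAP 3.5 governs.**

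| Column | QW days | Share, 7-day run-in | Share, 1-day run-in |
|---|---|---|---|
| QD | 91 | 91/210 = 43% | 91/204 = 45% |
| QW | 182 | 182/210 = 87% | 182/204 = 89% |

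**Where QW exposure is reported.**
- QW arm: 15 × 26 = 390 patient-weeks.
- QD arm: 15 × 13 = 195 patient-weeks.
- Total 585, of which 195/585 = 33% is under the QD heading. For arm splits (QD:QW) from 13:17 to 17:13 the share runs from 28% to 40%.
- The Day 1 to Week 14 table holds 15 × 13 = 195 QW patient-weeks, again 33%. The other 30 × 13 = 390 are open-label and appear only in the full-study table.

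**Can the open-label counts be recovered by subtracting one window from the other?** No, for two reasons.
- Each patient counts once per table. A patient with the same event in both the double-blind and open-label periods adds one to each table and vanishes from the difference.
- The remainder is not purely open-label. Outside Day 1 to Week 14 there are 210 − 91 = 119 days (113 with a 1-day run-in), of which 91 are open-label: 76% to 81%. The rest is QD run-in and follow-up.

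**Exposure and compliance.** SAP 4.5.1 defines one treatment duration, first dose to last dose, and two compliance formulas: doses/days × 100 for QD and doses × 7/days × 100 for QW. Suppose these were applied to whole-study groups, counting active doses with a 7-day run-in:
- QD sequence, fully adherent: 7 + 91 + 13 + 21 = 132 doses in 210 days. QD formula: 132/210 = 62.9%. QW formula: 132 × 7/210 = 440%.
- QW sequence, fully adherent: 7 + 26 + 21 = 54 doses. QW formula: 54 × 7/210 = 180%.

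Neither formula gives 100% for a perfectly adherent patient unless it is confined to time on its own regimen.

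**The case against.** The strongest reply is that the two rules need not conflict. SAP 2.1 sets the Full Analysis and Per Protocol Sets by randomised treatment and the Safety Set by treatment received, which is the ordinary as-randomised versus as-treated contrast for handling mis-dosing. On that reading patients go to the sequence they actually received, and SAP 3.5 governs every table that speaks of a group. SAP 4.1 does refer back to 3.5 for the groups. This largely stands: a reader might infer a flat contradiction, but the text supports only a missing statement of how the rules apply to patients who switch. The natural reading does not help the TEAE table, though, because it is the one that puts open-label QW time under QD.

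Second, a reader might infer that open-label events go unreported. They do not. The overall column of the full-study table contains them, and SAP 4.5.2 lists all AEs by patient; Protocol 9.3.3 asks for onset dates and treatment in those listings. What is missing is a summary that separates them from QD time and shows patients at risk.

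Third, it is tempting to say how far a true QW-to-QD difference would be diluted. The documents give no event rates, and the planned table shows percentages of patients counted once, not rates per unit of time, so they support no such figure.

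Fourth, much is untouched. In Day 1 to Week 14, group and regimen coincide. Injection site reactions are planned by formulation (Protocol 9.3.3, SAP 4.5.3), and by-visit tables can be read by period. Only the QW arm can supply 26 weeks of QW. SAP 4.5.1 also words its compliance formulas separately for QD and QW treatment, so a split may be intended; it is not defined.

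**Conclusion.** The point holds as a gap in tabulation and labelling. On the most natural reading, the full-study QD column is a QD-then-QW sequence with 43–45% of its time on QW. About a third of planned QW patient-weeks (195 of 585), from about half of the QW-exposed patients, sit under that heading. No TEAE summary separately shows the open-label period or all QW exposure. The shares of time depend only on the planned period lengths; the patient-week figures also assume 15 per arm and no dropout. The compliance figures are conditional on the formulas being applied to the whole study.

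It does not follow that the randomised comparison is compromised or that the primary PK analysis is affected. The full-study QW column, at 87–89% QW time, largely serves the secondary objective for patients randomised to QW. This is a worthwhile and inexpensive improvement to make before database lock.

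**What to change.** 1. In SAP 3.5, 4.5.1 and 4.5.2, label the full-study columns as sequences (QD then QW; QW then QW), and state how this grouping and the treatment-received rule of SAP 2.1 apply to patients who switch.
2. Add two TEAE tables: one for all QW exposure, blinded plus open-label, by regimen at onset, with patients at risk and patient-weeks; and one for the open-label period (Week 14 to Week 27) by prior arm. Fix in advance how events soon after a switch are assigned.
3. In SAP 4.5.1, report doses, mg, duration and compliance by regimen, applying each compliance formula only to time on that regimen and stating whether placebo injections count.
4. Keep Day 1 to Week 14 as the randomised comparison.

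Cost: SAP wording and a few more tables. No new data are needed, because SAP 4.5.2 already uses each patient's period start and end dates to subset AEs. The downside is that patients can appear under both regimens, so the by-regimen tables are not a randomised comparison and should say so.
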